16.7 Appendix 7: Opioid Oral Morphine mg Equivalents of Commonly Used Opioids

Opioid	30 mg morphine equivalent
butorphanol	4.3 mg/day
codeine	200 mg/day
dihydrocodeine	120 mg/day
fentanyl transdermal	12.5 mg/day
hydrocodone	30 mg/day
hydromorphone	7.5 mg/day
levorphanol tartrate	2.7 mg/day
meperidine HCl	300 mg/day
oxycodone	20 mg/day
oxymorphone	10 mg/day
pentazocine	81.1 mg/day
tapentadol	75 mg/day
tramadol	300 mg/day

Note that this list is not comprehensive. If an opioid is being used which is not in this list, please see the appropriate conversion factor below.

Opioid Oral Morphine Equivalent Conversion Factors^{a,b}

Type of Opioid (strength in units)	MME Conversion Factor
Buprenorphine film/tablet ^c (mg)	30
Buprenorphine patch ^d (mcg/hr)	12.6
Buprenorphine film (mcg)	0.03
Butorphanol (mg)	7
Codeine (mg)	0.15
Dihydrocodeine (mg)	0.25
Fentanyl buccal or SL tablets, or lozenge/troche ^e (mcg)	0.13
Fentanyl film or oral spray ^f (mcg)	0.18
Fentanyl nasal spray ^g (mcg)	0.16
Fentanyl patch ^h (mcg)	7.2
Hydrocodone (mg)	1
Hydromorphone (mg)	4
Levorphanol tartrate (mg)	11
Meperidine hydrochloride (mg)	0.1
Methadone ⁱ (mg)	3
> 0, ≤ 20	4
> 20, ≤ 40	8
> 40, ≤ 60	10
> 60	12
Morphine (mg)	1
Opium (mg)	1
Oxycodone (mg)	1.5
Oxymorphone (mg)	3
Pentazocine (mg)	0.37
Tapentadol ^j (mg)	0.4
Tramadol (mg)	0.1

CDC = Centers for Disease Control; CMS = Centers for Medicare and Medicaid Services; FDA = Food and Drug Administration; MAT = Medication Assisted Treatment; MME = morphine mg equivalent; OMS = Overutilization Monitoring System.

^a The MME conversion factor is intended only for analytic purposes where prescription data is used to calculate daily MME. It is to be used in the formula: Strength per Unit × (Number of Units/Days Supply) × MME conversion factor = MME/Day. This value does not constitute clinical guidance or recommendations for converting patients from one form of opioid analgesic to another. Please consult the manufacturer's full prescribing information for such guidance. Use of this file for the purposes of any clinical decision-making warrants caution.

- b National Center for Injury Prevention and Control. CDC compilation of benzodiazepines, muscle relaxants, stimulants, zolpidem, and opioid analgesics with oral morphine mg equivalent conversion factors, 2016 version. Atlanta, GA: Centers for Disease Control and Prevention; 2016. Available at <https://www.cdc.gov/drugoverdose/media/>. For more information, send an email to [contact].
- c Buprenorphine formulations with a FDA approved indication for MAT are excluded from Medicare's Overutilization Monitoring System's opioid overutilization reporting.
- d The MME conversion factor for buprenorphine patches is based on the assumption that 1 mg of parenteral buprenorphine is equivalent to 75 mg of oral morphine and that one patch delivers the dispensed micrograms per hour over a 24 hour day. Example: $5 \mu\text{g/hr buprenorphine patch} \times 24 \text{ hrs} = 120 \mu\text{g/day buprenorphine} = 0.12 \text{ mg/day} = 9 \text{ mg/day oral MME}$. In other words, the conversion factor not accounting for days of use would be 9/5 or 1.8.

However, since the buprenorphine patch remains in place for 7 days, we have multiplied the conversion factor by 7 ($1.8 \times 7 = 12.6$). In this example, MME/day for 4 5 $\mu\text{g/hr}$ buprenorphine patches dispensed for use over 28 days would work out as follows: Example: $5 \mu\text{g/hr buprenorphine patch} \times (4 \text{ patches}/28 \text{ days}) \times 12.6 = 9 \text{ MME/day}$. Please note that because this allowance has been made based on the typical dosage of 1 buprenorphine patch per 7 days, you should first change all Days Supply in your prescription data to follow this standard, i.e., Days Supply for buprenorphine patches = number of patches \times 7.

- e The MME conversion factor for fentanyl buccal tablets, sublingual tablets, and lozenges/troche is 0.13. This conversion factor should be multiplied by the number of micrograms in a given tablet or lozenge/troche.
- f The MME conversion factor for fentanyl film and oral spray is 0.18. This reflects a 40% greater bioavailability for films compared to lozenges/tablets and 38% greater bioavailability for oral sprays compared to lozenges/tablets.
- g The MME conversion factor for fentanyl nasal spray is 0.16, which reflects a 20% greater bioavailability for sprays compared to lozenges/tablets.
- h The MME conversion factor for fentanyl patches is based on the assumption that 1 mg of parenteral fentanyl is equivalent to 100 mg of oral morphine and that 1 patch delivers the dispensed micrograms per hour over a 24 hour day. Example: $25 \mu\text{g/hr fentanyl patch} \times 24 \text{ hrs} = 600 \text{ ug/day fentanyl} = 60 \text{ mg/day oral morphine mg equivalent}$.

In other words, the conversion factor not accounting for days of use would be 60/25 or 2.4.

However, since the fentanyl patch remains in place for 3 days, we have multiplied the conversion factor by 3 ($2.4 \times 3 = 7.2$). In this example, MME/day for 10 25 $\mu\text{g/hr}$ fentanyl patches dispensed for use over 30 days would work out as follows:

Example: $25 \mu\text{g/hr fentanyl patch} \times (10 \text{ patches}/30 \text{ days}) \times 7.2 = 60 \text{ MME/day}$. Please note that because this allowance has been made based on the typical dosage of 1 fentanyl patch per 3 days, you should first change all Days Supply in your prescription data to follow this standard, i.e., Days Supply for fentanyl patches = number of patches \times 3.

- i The CDC MME conversion factor to calculate morphine mg equivalents is 3. CMS uses this conversion factor when analyzing Medicare population opioid use. CMS uses the graduated methadone MME conversion factors to calculate MME within the OMS for identifying and reporting potential opioid overutilizers. https://www.cdc.gov/drugoverdose/pdf/calculating_total_daily_dose-a.pdf.
- j Tapentadol is a mu receptor agonist and norepinephrine reuptake inhibitor. Oral MMEs are based on degree of mu-receptor agonist activity, but it is unknown if this drug is associated with overdose in the same dose-dependent manner as observed with medications that are solely mu receptor agonists.

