27. Any other severe acute or chronic medical or psychiatric condition, including recent (within the past year) medical conditions (e.g., cardiovascular conditions, respiratory illnesses) that may increase the risk associated with study participation or investigational product administration or may interfere with the interpretation of study results and, in the judgment of the Investigator, sponsor or sponsor's designee, would make the patient inappropriate for entry into this study.
28. Investigational site staff members directly involved in the conduct of the trial and their family members, site staff members otherwise supervised by the Investigator, or patients who are employees of the sponsor or directly involved in the conduct of the trial.
29. Currently participating in, or who have participated in other interventional (drug or device) clinical study within 30 days or 5 half-lives of baseline, whichever is longer.
30. Recent (within the past 12 months) or active suicidal ideation or behavior based on patient responding "yes" to question 3, 4 or 5 on the C-SSRS.
31. Current or pending incarceration.
32. Current or pending compulsory detainment for treatment of either a psychiatric or physical (e.g., infectious disease) illness.
33. Currently taking a total daily dose of > 30 mg morphine or morphine equivalent (see [Appendix 7](#)).
34. Body mass index (BMI) \geq 40.0.

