
PROTOCOL SUMMARY, Main Criteria for Inclusion and Exclusion, Exclusion Criteria criterion 7, 23, and 27
 
Section 4.5, Exclusion Criteria, criterion 7, 23, and 27
	
Add:
 
7. Concomitant illness that, in the opinion of the investigator or the sponsor or their designee, is likely to require additional systemic glucocorticosteroid therapy during the study, (eg, asthma), is exclusionary
 
23. Any other laboratory test results that, in the opinion of the Investigator or the sponsor or sponsor's designee, might place a patient at unacceptable risk for participating in this study
 
27. Any other severe acute or chronic medical or psychiatric condition, including recent (within the past year) medical conditions (eg, cardiovascular conditions, respiratory illnesses) that may increase the risk associated with study participation or investigational product administration or may interfere with the interpretation of study results and, in the judgment of the investigator, sponsor or sponsor's designee, would make the patient inappropriate for entry into this study
	
To clarify that sponsor or designee can determine a patient is not eligible.

PROTOCOL SUMMARY, Main Criteria for Inclusion and Exclusion, Exclusion Criteria criterion 15
 
Section 4.5, Exclusion Criteria, criterion 15
	
Replace:
 
15. CD4+ count < 350/μL at screening
 
With:
 
15. CD4+ count < 150/μL at screening
	
Reduced based on safety data from MAD portion of the study.

PROTOCOL SUMMARY, Main Criteria for Inclusion and Exclusion, Exclusion Criteria criterion 22
 
Section 4.5, Exclusion Criteria, criterion 22
	
Replace:
 
22. Direct bilirubin > 1.5 \times ULN at screening (unless related to Gilbert's syndrome)
 
With:
 
22. Total bilirubin > 1.5 \times ULN at screening (unless related to Gilbert's syndrome)
	
Total bilirubin is tested at screening, but direct bilirubin is only tested when there is potential liver injury.

PROTOCOL SUMMARY, Main Criteria for Inclusion and Exclusion, Exclusion Criteria criterion 33
 
Section 4.5, Exclusion Criteria, criterion 33
	
Add:
 
33. Currently taking a total daily dose of > 30 mg morphine or morphine equivalent (see Appendix 7)
	
Opioid will mask SLE symptoms.

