
PROTOCOL SUMMARY, Main Criteria for Inclusion and Exclusion,
	
Add:
 
34. Body mass index (BMI) \geq 40.0
	
Added restriction due to increased co-morbidities

Section	Description of Changes	Rationale
Exclusion Criteria criterion 34		in patients with high BMI that will hinder SLE Assessments.
Section 4.5, Exclusion Criteria, criterion 34		
LIST OF ABBREVIATIONS	
Add:
 
ADL activities of daily living
 
BMI body mass index
 
NSAID nonsteroidal anti-inflammatory drug
	Terms added to protocol amendment.
Section 3.1.2.1, BOS161721 POC Dose Selection and Justification, Paragraph 5	
Replace:
 
The 120 mg dose will be communicated to site investigators participating in the POC Phase 2 portion, and to Institutional Review Boards (IRBs) and the Independent Ethics Committee (IEC).
 
With:
 
The 120 mg dose was communicated to site investigators participating in the POC Phase 2 portion, and to Institutional Review Boards (IRBs) and the Independent Ethics Committee (IEC).
	Protocol clarification.
Section 3.1.2.2, POC Study Design, Paragraph 2	
Replace:
 
As in the MAD part of the study, each patient in the POC portion may receive a total of 7 SC monthly doses of study drug on Days 0, 30, 60, 90, 120, 150, and 180. Assessments will be completed according to the Schedule of Assessments (Section 3.4).
 
With:
 
As in the MAD part of the study, each patient in the POC portion may receive a total of 7 SC monthly doses of study drug on Days 0, 30, 60, 90, 120, 150, and 180. Assessments will be completed according to the Schedule of Assessments (Table 1 and Table 4).
	Protocol clarification.
Section 3.4, Schedule of Assessments, Table 1	Delete:	Since Phase 1b MAD has completed, the Schedule of Assessments for Phase 1b MAD was moved to the Appendix.

Section	Description of Changes	Rationale

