 27. Any other severe acute or chronic medical or psychiatric condition, including recent (within the past year) medical conditions (eg, cardiovascular conditions, respiratory illnesses) that may increase the risk associated with study participation or investigational product administration or may interfere with the interpretation of study results and, in the judgment of the investigator, would make the patient inappropriate for entry into this study
 28. Investigational site staff members directly involved in the conduct of the trial and their family members, site staff members otherwise supervised by the investigator, or patients who are employees of the sponsor or directly involved in the conduct of the trial
 29. Currently participating in, or who have participated in other interventional (drug or device) clinical study within 30 days or 5 half-lives of baseline, whichever is longer
 30. Recent (within the past 12 months) or active suicidal ideation or behavior based on patient responding "yes" to question 3, 4, or 5 on the C-SSRS
 31. Current or pending incarceration
 32. Current or pending compulsory detainment for treatment of either a psychiatric or physical (eg, infectious disease) illness

Statistical Considerations

Below is a summary of the statistical methods. Further details can be found in [Section 8](#).

Two analyses are planned: 1) an interim analysis to select the POC dose based on the MAD data, and 2) a final analysis at study completion. Additionally, DMC safety analyses will be performed for each MAD cohort and throughout the POC to monitor patient safety as described in the DMC charter. An additional analysis may be performed for the MAD portion of the study when all MAD patients have completed the safety follow-up, or withdrawn from the study, and prior to the final analysis. Data from the POC part of the study will be excluded from this additional analysis.

Unless stated otherwise, statistical testing will only be performed on the POC data and will be done using 2-sided overall alpha of 0.10. Data will be summarized descriptively by treatment and overall for each study phase. For the MAD portion, BOS161721 will be summarized overall and by each dose level and placebo patients from each cohort will be combined.

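### Appendix 7 gives the 30 mg morphine equivalent of transdermal fentanyl as 12.5 mg/day; by the appendix's own factor it is 12.5 µg/hr (0.3 mg/day), so the printed unit is 41.7 times too high

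*Protocol*

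**What the plan says.** Exclusion 33 in section 4.5 excludes a patient who is "Currently taking a total daily dose of > 30 mg morphine or morphine equivalent" and points to Appendix 7. The summary of changes for V6.0, which introduced the criterion, gives the reason: "Opioid will mask SLE symptoms".

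Appendix 7 has two tables. The first lists, for 13 opioids, the daily dose taken as equal to 30 mg of morphine. Its fentanyl row is "fentanyl transdermal 12.5 mg/day". A note below sends the reader to the second table, of conversion factors, only when the opioid is absent from the first.

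Footnote h belongs to the fentanyl patch row of the second table. It assumes that "1 mg of parenteral fentanyl is equivalent to 100 mg of oral morphine" and that a patch delivers its labelled µg/hr over 24 hours. Its worked example takes a 25 µg/hr patch to 600 µg/day, hence 60 mg/day of oral morphine, and concludes that "the conversion factor not accounting for days of use would be 60/25 or 2.4". It then multiplies by 3, "since the fentanyl patch remains in place for 3 days", to reach the tabulated factor of 7.2.

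**The concern.** The row and the footnote cannot both be right. The footnote puts 60 mg of morphine at 0.6 mg/day of fentanyl, while the row puts half that amount of morphine at 12.5 mg/day.

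At stake is how exclusion 33 is applied to fentanyl-patch users. Read as printed, a 25 µg/hr patch (0.6 mg/day) uses 0.6/12.5 = 4.8% of the allowance, so the patient appears eligible. By footnote h that patient takes 60 mg/day of morphine equivalent, twice the limit, and should be excluded. Because fentanyl is in the first table, the note does not send a site on to the factor table and its footnote. The criterion exists to keep analgesia from hiding disease activity, so such an error would admit the kind of patient it was written to keep out.

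**Working it through.** **Inputs, all from Appendix 7**

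- Printed 30 mg equivalent: 12.5 mg/day (first table).
- Potency: 1 mg fentanyl = 100 mg oral morphine (footnote h).
- Patch factor per µg/hr before days of wear: 60/25 = 2.4 (footnote h).
- Patch factor including 3 days of wear: 2.4 × 3 = 7.2 (second table and footnote h).
- Formula: strength × (units / days supply) × factor = morphine mg equivalent (MME) per day (footnote a).

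**The appendix's own example first.** 25 µg/hr × 24 h = 600 µg/day = 0.6 mg/day, and 0.6 × 100 = 60 mg/day. With the formula, 25 × (10/30) × 7.2 = 60 MME/day. Footnote h is consistent with itself.

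**The dose equal to 30 mg of morphine, by three routes**

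1. Patch factor: 30/2.4 = 12.5 µg/hr; 12.5 × 24 = 300 µg/day = 0.3 mg/day.
2. Potency: 30/100 = 0.3 mg/day.
3. Formula, checking 12.5 µg/hr: 12.5 × (10/30) × 7.2 = 30 MME/day.

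All three agree on 12.5 µg/hr, or 0.3 mg/day.

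**The printed row taken literally**

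- 12.5 mg/day × 100 = 1,250 mg of morphine per day, against 30 mg intended.
- 12.5/0.3 = 41.7-fold too high.
- 12,500 µg / 24 h = 520.8 µg/hr, which is 520.8/25 = 20.8 patches of 25 µg/hr worn at once.

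**Could another reading rescue the unit?** No. Using the factor that includes wear time gives 30/7.2 = 4.17, not 12.5. If only a µ had been lost in reading the PDF, the entry would be 12.5 µg/day, which is 0.0125 × 100 = 1.25 mg of morphine. The entry is correct only as µg/hr, and a single misread character would not also turn a rate per hour into a rate per day. V6.0 carries the same row.

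**Control: the other 12 rows (printed dose × the appendix's factor)**

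| Opioid | mg/day | Factor | Morphine, mg |
|---|---|---|---|
| Butorphanol | 4.3 | 7 | 30.1 |
| Codeine | 200 | 0.15 | 30.0 |
| Dihydrocodeine | 120 | 0.25 | 30.0 |
| Hydrocodone | 30 | 1 | 30.0 |
| Hydromorphone | 7.5 | 4 | 30.0 |
| Levorphanol | 2.7 | 11 | 29.7 |
| Meperidine | 300 | 0.1 | 30.0 |
| Oxycodone | 20 | 1.5 | 30.0 |
| Oxymorphone | 10 | 3 | 30.0 |
| Pentazocine | 81.1 | 0.37 | 30.0 |
| Tapentadol | 75 | 0.4 | 30.0 |
| Tramadol | 300 | 0.1 | 30.0 |

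Every other row agrees within rounding, so the fault is confined to fentanyl.

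**The case against.** The strongest case against is about weight, not fact. The binding rule, more than 30 mg of morphine equivalent, is stated correctly; only one cell of a conversion aid is wrong. The 41.7-fold error bites only if a site converts patch strength from µg/hr to mg/day and then accepts a limit of about 21 patches. A site that compares patch strength in µg/hr with 12.5 decides correctly, and footnote h says outright that 25 µg/hr is 60 mg/day. No site decides alone: sections 4.3, 5.1, 5.2 and 10 give eligibility to the medical monitor and central review. Section 4.6 asks patients to refrain from opiates for 12 hours before each visit after screening, which fits poorly with a patch worn for 3 days. No document shows that any patch user was screened or enrolled.

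Most of this stands, and it is why the reach is called small. Two parts are weaker than they look. Footnote h is not where the protocol sends a reader for fentanyl. And the reviewers are given no other conversion table in the protocol, so their check is not independent of the error. That a misreading is unlikely does not make the printed threshold right.

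**Conclusion.** The row is wrong as written. On the appendix's own potency and delivery assumptions, 30 mg of oral morphine corresponds to transdermal fentanyl 12.5 µg/hr, or 0.3 mg/day; the printed unit overstates the limit 41.7-fold on a literal reading. No figure from outside the protocol is needed.

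The effect is limited to screening fentanyl-patch users under exclusion 33. Their number is not stated and is probably very small. The error should be corrected because it sits in a table that an eligibility criterion relies on and because section 4.8 allows no deviation from the criteria. It does not threaten the trial's conclusions.

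**What to change.** Change the fentanyl cell in the first table of Appendix 7 to 12.5 µg/hr (0.3 mg/day). The cost is one table cell.

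Optionally, look through the concomitant-medication records already on the eCRF for fentanyl-patch users whose total daily opioid dose at entry exceeded 30 mg of morphine equivalent. Limit this to patients enrolled under V6.0 or later, since the V5.0 exclusion list ends at criterion 32. Use the total dose, as the criterion does: a 12.5 µg/hr patch plus oxycodone 5 mg/day comes to 12.5 × 2.4 + 5 × 1.5 = 37.5 mg and is excluded, although the patch alone is not.

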16.8 Appendix 8: Schedule of Assessments - Phase 1b Multiple Ascending Dose

Table 4. Schedule of Assessments - Phase 1b - Multiple Ascending Dose

	Screen ^a	Enroll	Treatment Period Follow-Up											Safety Follow-Up		
Days	-28 to -1	0	7 (± 1)	15 (± 3)	30 (± 3)	44 (± 3)	60 (± 3)	90 (± 3)	120 (± 3)	150 (± 3)	180 (± 3)	187 (± 3)	195 (± 3)	210 (± 3)	240 (± 3)	270 (± 3)
Visit Number	1	2	--	3	4	5	6	7	8	9	10	--	--	11	12	13
GENERAL ASSESSMENTS																
Informed consent	X															
Inclusion/Exclusion criteria	X															
Medical history	X															
Demographics	X															
SLICC Criteria for SLE	X															
Concomitant medication ^b	X	X	X	X	X	X	X	X	X	X	X	X	X	X	X	X
Randomization ^c		X														
BOS161721 or placebo dosing		X			X		X	X	X	X	X					
SAFETY ASSESSMENTS																
Full physical exam	X	X														

^a Screening assessments will be performed over more than 1 visit.

^b Concomitant use of oral corticosteroids: A maximum daily dose of 30 mg/day of oral CS will be acceptable for eligibility for the study, however, the daily dose must be tapered down to a maximum of 10 mg/day for at least 5 days prior to Day 0 (randomization day). See [Section 4.6.1](#) for further details.

^c Randomization should occur after patient eligibility has been confirmed by central eligibility review.

Table 4. Schedule of Assessments - Phase 1b - Multiple Ascending Dose

	Screen ^a	Enroll	Treatment Period Follow-Up											Safety Follow-Up		
Days	-28 to -1	0	7 (± 1)	15 (± 3)	30 (± 3)	44 (± 3)	60 (± 3)	90 (± 3)	120 (± 3)	150 (± 3)	180 (± 3)	187 (± 3)	195 (± 3)	210 (± 3)	240 (± 3)	270 (± 3)
Visit Number	1	2	--	3	4	5	6	7	8	9	10	--	--	11	12	13
Chest x-ray ^d	X															
C-SSRS	X	X						X			X					
AEs and SAEs		X	X	X	X	X	X	X	X	X	X	X	X	X	X	X
12-lead ECG ^e	X	X			X			X								X
Injection site reaction assessment		X ^f	X		X		X	X	X	X	X	X	X	X	X	X
Targeted physical examination				X	X	X	X	X	X	X	X			X	X	X
Vital signs (BP, HR, and temperature) ^g	X	X		X	X	X	X	X	X	X	X			X	X	X
EFFICACY ASSESSMENTS																
BILAG-2004 Index	X	X			X		X	X	X	X	X			X	X	X

^d If patients have had a TB test and chest x ray within 3 months prior to screening, then these assessments do not need to be repeated during screening. The results of TB screening, which includes the QuantiFERON®-TB Gold In-Tube (QFT-G) test and a chest x-ray, conducted in the 3 months prior to screening or during the screening period must be documented in study records prior to randomization (Day 0).

^e ECGs will be performed after the patient has been supine for at least 5 minutes. On days of PK blood draws, the ECG will be collected before scheduled PK blood draws.

^f Injection site reaction assessments to be performed at 2 hours postdose.

^g Vital signs will be assessed after the patient has been supine and at rest ≥ 5 minutes. Vital signs will be assessed on Day 0 at predose and at 1 and 2 hours (±15 minutes) postdose, as well as on each of the scheduled outpatient days in the table above (excluding PK-only site visits at Days 7, 187, and 195). When the timing of these measurements coincides with a blood collection, vital signs should be obtained prior to the time of the blood collection

Table 4. Schedule of Assessments - Phase 1b - Multiple Ascending Dose

Days	Screen ^a	Enroll	Treatment Period Follow-Up											Safety Follow-Up		
	-28 to -1	0	7 (± 1)	15 (± 3)	30 (± 3)	44 (± 3)	60 (± 3)	90 (± 3)	120 (± 3)	150 (± 3)	180 (± 3)	187 (± 3)	195 (± 3)	210 (± 3)	240 (± 3)	270 (± 3)
Visit Number	1	2	--	3	4	5	6	7	8	9	10	--	--	11	12	13
SLEDAI-2K ^h	X	X			X		X	X	X	X	X			X	X	X
PGA of disease activity	X	X			X		X	X	X	X	X			X	X	X
ACR-28 joint count	X	X			X		X	X	X	X	X			X	X	X
CLASI	X	X			X		X	X	X	X	X			X	X	X
CCI		X			X		X	X	X	X	X			X	X	X
SLICC/ACR Damage Index		X									X					
CCI		X			X		X	X	X	X	X			X	X	X
LABORATORY ASSESSMENTS																
CD4+ count	X	X		X	X	X		X			X					
Clinical laboratory assessments (hematology and clinical chemistry) ⁱ	X	X			X	X	X	X	X	X	X			X	X	X
Coomb's test direct ^j	X	X			X		X	X	X	X	X			X	X	X
Total IgG and IgM	X	X		X	X	X		X			X					
Plasma CCI	X	X			X		X	X	X	X	X			X	X	X
Plasma CCI & CCI		X		X	X		X	X			X					

^h SLEDAI-2K should be done before randomization and dosing on Day 0 as SLEDAI-2K < 6 is exclusionary

ⁱ Clinical laboratory assessments will include a fasting glucose and lipid panel, with exception of screening (Visit 1) which will be non-fasting

^j When clinically indicated for hemolytic anemia

Table 4. Schedule of Assessments - Phase 1b - Multiple Ascending Dose

Days	Screen ^a	Enroll	Treatment Period Follow-Up											Safety Follow-Up		
	-28 to -1	0	7 (± 1)	15 (± 3)	30 (± 3)	44 (± 3)	60 (± 3)	90 (± 3)	120 (± 3)	150 (± 3)	180 (± 3)	187 (± 3)	195 (± 3)	210 (± 3)	240 (± 3)	270 (± 3)
Visit Number	1	2	--	3	4	5	6	7	8	9	10	--	--	11	12	13
Whole blood for leukocyte immunophenotype		X		X	X		X	X			X					
ADA ^k		X		X	X		X	X			X					X
nAb ^l							X				X					
pSTAT3 ^m		X			X	X	X	X								
CCI [REDACTED]		X		X				X			X					X
CCI [REDACTED]		X														
CCI [REDACTED]																
[REDACTED]	X	X			X		X	X	X	X	X			X ⁿ	X ⁿ	X ⁿ
CRP	X							X								X
Serum pregnancy test (women)	X															

^k Blood samples for ADA analysis will be collected up to Day 90 from all patients. Subsequent ADA samples will be collected from all patients, but only assayed (analyzed) if the patient had a positive ADA on Day 90

^l nAb is collected for all patients, though will only be analyzed by central lab if patient is positive for ADA at Day 90

^m Predose (trough) samples only

ⁿ Antibodies and autoantibodies (CCI [REDACTED]) will not be analyzed during safety follow-up visits

Table 4. Schedule of Assessments - Phase 1b - Multiple Ascending Dose

Days	Screen ^a	Enroll	Treatment Period Follow-Up											Safety Follow-Up		
	-28 to -1	0	7 (± 1)	15 (± 3)	30 (± 3)	44 (± 3)	60 (± 3)	90 (± 3)	120 (± 3)	150 (± 3)	180 (± 3)	187 (± 3)	195 (± 3)	210 (± 3)	240 (± 3)	270 (± 3)
Visit Number	1	2	--	3	4	5	6	7	8	9	10	--	--	11	12	13
FSH (postmenopausal women)	X															
Urine pregnancy test (women) ^o		X			X		X	X	X	X	X					X
TB test (QuantiFERON [®] -TB Gold In-Tube) ^d	X															
Serology (hepatitis B and C, HIV-1/2 combination)	X															
Stool sample ^p	X															
Spot urine for protein/creatinine ratio	X	X			X		X	X	X	X	X			X	X	X
Urinalysis	X	X			X		X	X	X	X	X			X	X	X
PK Labs																
Predose		X			X		X	X	X	X	X					
Predose PK Window		60 m			± 3 d		± 3 d	± 3 d	± 3 d	± 3 d	± 3 d					
Postdose		X ^q	X	X	X ^q							X ^q	X	X	X	X

^o Urine pregnancy test will be collected on WOCBP prior to study drug administration on dosing visits

^p Cryptosporidium test is required at screening. If a patient develops diarrhea during the study a stool sample must be provided to test for ova, parasites, and cryptosporidium

^q Postdose samples will be collected at 4, 8, and 24 hours after study drug administration on Days 0, 30, and 180

Table 4. Schedule of Assessments - Phase 1b - Multiple Ascending Dose

	Screen ^a	Enroll	Treatment Period Follow-Up											Safety Follow-Up		
Days	-28 to -1	0	7 (± 1)	15 (± 3)	30 (± 3)	44 (± 3)	60 (± 3)	90 (± 3)	120 (± 3)	150 (± 3)	180 (± 3)	187 (± 3)	195 (± 3)	210 (± 3)	240 (± 3)	270 (± 3)
Visit Number	1	2	--	3	4	5	6	7	8	9	10	--	--	11	12	13
Postdose PK Window		4 h ± 30 m 8 h ± 45 m 24 h ± 60 m	± 1 d	± 3 d	4 h ± 30 m 8 h ± 45 m 24 h ± 60 m						4 h ± 30 m 8 h ± 45 m 24 h ± 60 m	± 3 d	± 3 d	± 3 d	± 3 d	± 3 d

Abbreviations: ACR = American College of Rheumatology; ADA= anti-drug antibody; AE = adverse event; APL = antiphospholipid; BILAG = British Isles Lupus Assessment Group; BP = blood pressure; CD4+ = cluster of differentiation 4; CLASI = Cutaneous Lupus Area and Severity Index; CRP = C-reactive protein; C-SSRS = Columbia Suicide Severity Rating Scale; ECG = electrocardiogram; **CCI**; **CCI**; FSH = follicle stimulating hormone; HR = heart rate; HIV = human immunodeficiency virus; IgG = immunoglobulin G; IgM = immunoglobulin M; IL-21 = interleukin 21; nAb = neutralizing antibody; PGA = Physician’s Global Assessment; PK = pharmacokinetic; pSTAT3 = phosphorylated signal transducer and activator of transcription 3; SAE = serious adverse event; **CCI**; SLEDAI-2K = SLE Disease Activity Index 2000; SLICC = Systemic Lupus International Collaborating Clinics; **CCI**; **CCI**; TB = tuberculosis.

